### 7.3.1 Inclusion Criteria

Individuals eligible to participate in this study must meet all of the following criteria:

- 1) Diagnosis of Glut1 DS confirmed by *SLC2A1* mutation
- 2) Males and females at least 1 year of age at the time of informed consent
- 3) Average of at least 2 observable seizures (generalized or partial-onset [simple partial motor, complex partial, absence, or secondarily generalized] seizures) in 4 weeks over the last 24 weeks, by subject or caregiver report
- 4) At least 2 observable seizures (generalized or partial-onset [simple partial motor, complex partial, or secondarily generalized] seizures) in 4 weeks during the baseline period, with no 3-week seizure-free period during the Baseline Period OR absence seizures documented on Screening EEG
- 5) Continuing to have seizures despite a prior or current use of at least 1 AED
- 6) Allowed to be on up to 3 concomitant AEDs that must have been stable in dose at least 2 weeks prior to the beginning of screening and anticipated to remain stable in dose through the end of the 8-week, placebo-controlled Treatment Period
- 7) Not on, or not fully compliant with a prescribed diet plan (e.g. KD)
- 8) Plasma level of beta-hydroxybutyrate (BHB)  $\leq 1$  mmol/L (non-fasting) at Screening
- 9) Provide written or verbal assent (if possible) and written informed consent by a legally authorized representative after the nature of the study has been explained, and prior to any research-related procedures
- 10) Must, in the opinion of the investigator, be willing and able to complete all aspects of the study, comply with accurate completion of the seizures diary, and likely to complete the 8-week, placebo-controlled, Treatment Period
- 11) Females of childbearing potential must have a negative pregnancy test at Screening, be willing to use an acceptable method of contraception, and have additional

pregnancy tests during the study. Females considered not of childbearing potential include those who have not reached menarche, had total hysterectomy, have been in menopause for at least two years, or have had tubal ligation at least one year prior to Screening.

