5.6 Classification of Subjects at Randomization by Seizure Type

Classification of subjects is used to derive the primary efficacy endpoint and to define which subjects are included in secondary endpoint analyses of specific seizure types. At the Randomization Visit, subjects can be classified according to the types of seizures that are recorded on the diary as follows:

- **Observable Seizures Subject:** a subject who meets any of the following:
 - Observable Seizure Frequency (types A, B, C, D, E, F, G, H, I, J, K and L; see Section 5.7.5) greater than or equal to 4 at Randomization
 - Observable Seizure Frequency less than 4 at Randomization and Absence Seizure Frequency less than 4 at Randomization
- **Absence Seizures Subject:** a subject who meets any of the following:
 - has seizure types M, N, O or P (see Section 5.7.5) recorded on the seizure diary during the Baseline Period
 - has absence seizures documented on the Screening EEG
 - Absence Seizure Frequency (see Section 5.7.2) greater than 0 at Randomization

All subjects will either be an Observable Seizures Subject, an Absence Seizures Subject, or both. Since there is potential overlap, the following definitions are used to classify randomized subjects into three mutually exclusive groups:

- **Observable Seizures Only Subject:** a subject who is an Observable Seizures Subject *but not an Absence Seizure Subject*
- **Absence Seizures Only Subject:** a subject who is an Absence Seizures Subject *but not an Observable Seizure Subject*
- **Both Seizures Subject:** a subject who is both an Observable Seizures Subject and an Absence Seizure Subject

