5.7.4 Seizure Response

Seizure response is defined as a percent reduction from baseline in seizure frequency greater than or equal to 50%.

Observable seizure response, at least 50% reduction from baseline in frequency of observable seizures measured by diary, is defined as percent reduction in observable seizure frequency greater than or equal to 50%.

Absence seizure response, at least 50% reduction from baseline in frequency of absence seizures measured overnight by EEG, is defined as percent reduction in absence seizure frequency greater than or equal to 50%.

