7 DATA HANDLING AND ACCEPTANCE

7.1 Handling of Missing and Incomplete Data

Missing clinical outcome data can occur for multiple reasons, including missed subject visits and scales or measures with missing item scores. Missing and incomplete data will be identified through a review of tables and listings for this study. Missing and incomplete data will be identified for investigation and possible resolution by Data Management prior to the study database lock.

Unless otherwise specified, for missing assessments for an individual subject, these data would remain as missing. When a change from baseline is assessed, only subjects with a baseline and at least one post baseline measurement will be included in the analysis.

For primary and secondary analyses related to reduction in seizures from baseline to Week 8, imputation will be used to enable inclusion in analyses of all subjects in the Efficacy Analysis Set, the Efficacy Analysis Set – Observable Seizures and the Efficacy Analysis Set – Absence Seizures.

- For observable seizures subjects who have incomplete diary data during the Baseline Period but at least one day complete, observable seizure frequency will be calculated by averaging over the days with complete diary data. The same rule will be used for the Double-Blind Placebo-Controlled Treatment Period. Note that this also applies to subjects who terminate early.
- For absence seizures subjects who have incomplete EEG at either Randomization or Week 8, absence seizure frequency will be calculated by averaging over the time that is complete, even if the EEG is not done overnight.
- For subjects who have completely missing data for either Randomization or Week 8, a reduction from baseline in the natural logarithm of seizure frequency (+ 1) value of zero will be imputed for the response variable in any analyses of reduction from baseline, and non-response will be imputed for the response variable in any analyses of seizure response. For subjects who have completely missing data for Randomization, the Week 8 value will be imputed if available for the baseline covariate; if both Randomization and Week 8 are missing then the average baseline value of the subjects with complete data in the same treatment group will be imputed for the baseline covariate. In additional analyses related to reduction in seizures, two alternate methods will be implemented:

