 - the average reduction from baseline in the logarithm of seizure frequency (+ 1) of the subjects with complete data in the same treatment group will be imputed for the response variable in any analyses of reduction from baseline; and response will be imputed as yes if the imputed reduction from baseline is greater than or equal to the natural logarithm of 2 and no otherwise in any analyses of seizure response
 - no imputation, or complete case analysis – these data would remain as missing.

Imputation will not be used for analyses involving the open label period.

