8 STATISTICAL METHODS OF ANALYSIS

8.1 General Principles

During the Double-Blind Placebo-Controlled Treatment Period, efficacy analyses will be based on the Efficacy Analysis Set or the Per Protocol Analysis Set. During the open label period, efficacy analyses will be based on the Extension Set. Safety analyses will be based on the Safety Analysis Set. Unless stated otherwise, statistical tests will be 1-sided hypothesis tests performed at the 5% level of significance and confidence intervals will be 2-sided 90% confidence intervals. Continuous variables will be summarized by number of subjects and mean, standard deviation (SD), median, minimum, and maximum values. Categorical variables will be summarized by number and percentage of subjects.

Analyses and summaries by study period will be done for the following time periods:

- Double-blind placebo-controlled treatment period: after the date of the randomization visit until the date of the week 8 visit
- Open-label extension period: after the date of the week 8 visit until the date of the week 52 visit
- Dose exploration period: after the date of the week 26 visit until the date of the week 36 visit

Overall analyses and summaries will include all subjects and ignore treatment assignment.

For logarithmic transformations of seizure frequency, the natural logarithm will be used and a value of 1 will be added prior to performing the transformation.

For analyses and summaries of subjects while taking UX007, the time while taking placebo will be excluded and the original baseline will be used for all subjects regardless of which treatment was taken during the double-blind placebo-controlled treatment period.

Graphical displays of select study endpoints will be completed and include both observed study data and modeled analyses. Arithmetic means, least square means (LSM), and appropriate measure of dispersion (e.g., standard deviation, standard error) or confidence intervals may be displayed in figures.

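### The alternate imputation in SAP 7.1 scores response at a ln 2 fall in ln(frequency + 1), which is stricter than the 50% rule of SAP 5.7.4 and can turn imputed responders into non-responders

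*SAP*

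**What the plan says.** SAP 5.7.4: "Seizure response is defined as a percent reduction from baseline in seizure frequency greater than or equal to 50" percent. SAP 5.7.3 computes that percentage from the raw frequencies, with nothing added.

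For the log scale, SAP 8.1 says that "the natural logarithm will be used and a value of 1 will be added prior to performing the transformation".

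For completely missing Randomization or Week 8 data, SAP 7.1 gives a main rule for the response endpoints: "non-response will be imputed for the response variable in any analyses of seizure response". It continues: "In additional analyses related to reduction in seizures, two alternate methods will be implemented". One of these is complete case. The other imputes "the average reduction from baseline in the logarithm of seizure frequency (+ 1) of the subjects with complete data in the same treatment group", and for the response endpoints "response will be imputed as yes if the imputed reduction from baseline is greater than or equal to the natural logarithm of 2".

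SAP 8.6.4 calls for the alternate methods for all endpoints involving seizures. Table 6 lists three logistic-regression tables under the alternate imputation method: all-seizure, observable seizure and absence seizure response.

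**The concern.** The ln 2 cutoff is the natural translation of a 50% reduction only if the logarithm is taken of the frequency alone. The SAP takes the logarithm of frequency plus 1, so a fall of ln 2 halves f + 1 rather than f, and a larger reduction in f is needed to reach it. Subjects with data are scored on raw frequency and imputed subjects on the shifted scale, within the same logistic model.

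The gap is widest at low baselines, and the design admits them. Protocol 7.3.1 (criteria 3 and 4) sets the diary entry level at 2 observable seizures in 4 weeks. SAP 3.4 stratifies at 8 per 4 weeks. One route to being an Observable Seizures Subject in SAP 5.6 is "Observable Seizure Frequency less than 4 at Randomization and Absence Seizure Frequency less than 4 at Randomization".

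What is at stake is the value of the sensitivity analysis. The main analysis already imputes non-response. Whenever both arm means fall below ln 2, the alternate method imputes the same responses as the main analysis, and their agreement tells the reader nothing about robustness. A cutoff that is too strict makes this happen more often.

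**Working it through.** **Inputs.** Baseline frequency fB and Week 8 frequency fT, in the unit of the endpoint (per 28 days for the diary, SAP 5.7.1; per 24 hours for EEG, SAP 5.7.2). Imputed reduction d = arm mean of ln(fB + 1) − ln(fT + 1), one value per arm and endpoint (SAP 7.1). Cutoff ln 2 = 0.6931 (SAP 7.1). Response: (fB − fT)/fB ≥ 50% (SAP 5.7.3 and 5.7.4).

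**Step 1: where the cutoff would be right.** Without the +1, ln(fB/fT) ≥ ln 2 gives fT ≤ fB/2, which is exactly a 50% reduction at every baseline.

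**Step 2: what it means with the +1.** (fB + 1)/(fT + 1) ≥ 2 gives fT ≤ (fB − 1)/2, so the percent reduction must be at least 50% × (1 + 1/fB). For example, at fB = 4: 50% × 1.25 = 62.5%.

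**Step 3: the value of d that equals a 50% reduction.** Setting fT = fB/2 gives d = ln[(fB + 1)/(fB/2 + 1)]. For example, at fB = 4: ln(5/3) = 0.511.

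| fB | Reduction equivalent to ln 2 | d equal to a 50% reduction | Range of d that misclassifies |
|---|---|---|---|
| 2 | 75% | 0.405 | 0.405 to 0.693 |
| 4 | 62.5% | 0.511 | 0.511 to 0.693 |
| 8 | 56.25% | 0.588 | 0.588 to 0.693 |
| 20 | 52.5% | 0.647 | 0.647 to 0.693 |
| 100 | 50.5% | 0.683 | 0.683 to 0.693 |

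**Step 4: direction.** 50% × (1 + 1/fB) exceeds 50% at every positive baseline, so reaching ln 2 always implies a reduction of at least 50%. The error runs only from responder to non-responder. A numerical check on 1,000,000 fB/fT pairs agreed: no pair met ln 2 with a reduction under 50%, while 89,255 pairs with at least 50% failed it. Those counts depend on the simulated range and are not an error rate for this trial.

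**Step 5: an example.** An imputed d implies a reduction of (1 − e^−d)(1 + 1/fB). At d = 0.60, 1 − e^−0.60 = 0.451, which implies 67.7% at fB = 2, 56.4% at 4, 50.8% at 8 and 47.4% at 20. The SAP rule scores all four as non-response. This is wrong for the first three and right for the last.

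**Step 6: how large an arm effect clears the cutoff.** The documents give no baseline distribution, so the baseline sets are assumptions. Every complete subject in the arm is given the same percent reduction.

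| Assumed baselines | Mean d at 50% | at 55% | at 60% | at 65% |
|---|---|---|---|---|
| 2, 3, 4, 4, 6, 8 | 0.507 | 0.576 | 0.650 | 0.730 |
| 4, 8, 12, 20, 28 | 0.605 | 0.692 | 0.787 | 0.893 |
| 50, 100, 200, 400 | 0.684 | 0.787 | 0.903 | 1.033 |

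At a uniform 50% reduction every complete subject is a responder, yet the arm mean is below 0.693 at any baseline, so every imputed subject in that arm is a non-responder. In the low-baseline set this persists at 60% and has ended by 65%; in the high-baseline set it has ended by 55%. SAP 3.5 sizes the trial on a 50% between-group difference. With little change on placebo, that puts the UX007 arm near this region.

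**The case against.** The strongest reply is that very little depends on the rule. It applies only when Randomization or Week 8 data are completely missing. One complete diary day or any evaluable EEG time takes a subject out of it, and SAP 7.1 applies the diary rule to early terminators too. Neither document suggests how many of about 40 subjects would qualify. The rule sits in one of two alternate methods for secondary endpoints, and its error is towards non-response, which the main analysis imputes anyway. All of this stands and limits the point to a minor one. It does not make the cutoff agree with SAP 5.7.4.

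Three stronger readings are tempting, and the documents do not support them:

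- *The rule misclassifies imputed subjects as a matter of course.* It does so only when the arm mean falls in the range shown for the subject's baseline. Outside that range, the SAP rule and the 50% rule agree at any positive baseline.
- *A subject with a baseline below 1 can never be imputed a responder.* No single subject with fB below 1 could show a fall of ln 2, but SAP 7.1 compares the arm mean, not the subject's own value, with ln 2. If the arm mean reaches ln 2, a subject with baseline 0.5 is imputed as a responder. Back-transformation agrees: 1.5/2 − 1 = −0.25, floored at 0, a 100% reduction.
- *Each imputed subject faces a threshold that depends on baseline.* The threshold applied is fixed at ln 2; only the percent reduction it stands for varies. All imputed subjects in an arm get the same status within an endpoint analysis. That coarseness comes from imputing a group mean and would remain with any fixed cutoff.

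**Conclusion.** The rule is wrong as written, and the matter is minor. The ln 2 cutoff does not implement the 50% definition of response once 1 is added before taking logs. It stands for 75%, 62.5%, 56.25% and 52.5% at baselines of 2, 4, 8 and 20, and is practically the same as 50% at 100. It can misclassify imputed subjects, in one direction only, when the arm mean lies in the ranges shown above.

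The effect is confined to the three alternate-imputation response tables. A reader might infer that the primary result or the main response results are in doubt. They are not: the primary ANCOVA has no response cutoff, the main response analyses impute non-response, and the complete-case analyses impute nothing.

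The algebra rests on no assumption beyond the SAP's own definitions. The practical size depends on the baseline distribution, the arm means and the number of subjects with completely missing data, none of which the documents give. The SAS code in Appendix D is redacted, so the programmed rule could not be compared with the text.

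**What to change.** In SAP 7.1, replace the ln 2 cutoff by the 50% rule of 5.7.4, applied after back-transforming the imputed arm-mean reduction d:

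- Week 8 missing: fT = max(0, (fB + 1)·exp(−d) − 1), with the subject's own fB.
- Randomization missing, Week 8 observed: keep the observed fT and use fB = (fT + 1)·exp(d) − 1, with a negative result treated as zero. SAP 7.1 carries the Week 8 value into the baseline covariate for these subjects. Using that value as fB here would produce a new Week 8 frequency that contradicts the observed one.
- Both missing: take fB from the arm-average baseline that SAP 7.1 already specifies, saying whether the average is on the raw or the log scale, then compute fT as in the first case.
- Baseline zero: percent reduction is undefined, so score non-response. This can arise for the absence endpoint, because SAP 5.6 lets a subject qualify through diary codes or the Screening EEG with no absence seizures on the Randomization EEG.

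The cost is a short paragraph of SAP text and a few lines of code for three sensitivity tables. No data collection, primary analysis or main secondary analysis changes.

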7.2 Missing Date Imputation Rules

The following conventions will be used to impute missing portions of dates for adverse events and concomitant medications.

1. Start Dates

- a. If the year is unknown, then the date will not be imputed and will be assigned a missing value.
- b. If the month is unknown, then:
 - i. If the year matches the first dose date year, then impute the month and day of the first dose date.
 - ii. Otherwise, assign “January.”
- c. If the day is unknown, then:
 - i. If the month and year match the first dose date month and year, then impute the day of the first dose date.
 - ii. Otherwise, assign the first day of the month.

2. Stop Dates

- a. If the year is unknown, then the date will not be imputed and will be assigned a missing value.
- b. If the month is unknown, then assign “December.”
- c. If the day is unknown, then assign the last day of the month.

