5.4 Dosing Compliance

Number of days during a period is calculated as (end of period date – first dose date + 1) for the titration and treatment periods, and (end of period date – week 8 visit date + 1) for the extension period. Percent of days missed for a period is $100 \times (\text{number of days during the period with dose non-compliance}) / (\text{number of days during the period})$.

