8.7.1 Adverse Events

Adverse Events will be assessed at all visits and throughout the course of the study. An AE will be considered a treatment emergent adverse event (TEAE) if it occurs or worsens in severity on or after the date of the first dose of study drug. An AE will be considered a UX007 emergent adverse event if it occurs or worsens in severity on or after the first date of

first dose of UX007 during the study. It is expected that the date of first dose of UX007 during the study will be the date of Randomization visit for the UX007 group and the date of Week 8 visit for the placebo group; however, the date of first UX007 dose actually received will be used.

UX007 emergent AEs will be summarized by SOC and preferred term during the period exposed to UX007 by treatment group and overall for all subjects who receive UX007. TEAEs will be summarized by SOC and preferred term during the course of the study by treatment group and overall for all subjects who receive study drug.

Exposure adjusted event incidence, defined as total number of occurrences of an event summed across all subjects in the group divided by the total observed time for events for subjects in the group, will be summarized for TEAEs and UX007 emergent AEs by SOC and preferred term by treatment group and overall.

During the double-blind placebo-controlled period; TEAEs will be summarized by treatment group and overall, and UX007 emergent AEs will be summarized by treatment group and overall. If no placebo subjects also receive UX007 during the double-blind placebo-controlled period, then there will only be one group for UX007 emergent AEs during the double-blind placebo-controlled period. During the open-label extension period, TEAEs and UX007 emergent AEs will both be summarized by treatment group and overall.

A high-level safety summary will display the numbers of subjects who experience one or more AEs in each of the following categories:

- All TEAEs and UX007 emergent AEs
- All treatment related TEAEs and UX007 emergent AEs
- Serious TEAEs and UX007 emergent AEs
- All treatment related SAEs and UX007 emergent SAEs
- Grade 3/4 TEAEs and UX007 emergent AEs
- TEAEs and UX007 emergent AEs leading to study discontinuation
- Fatal TEAEs and UX007 emergent AEs
- TEAEs and UX007 emergent AEs in the GI SMQ (see [Appendix C](#))
- Related TEAEs and UX007 emergent AEs in the GI SMQ

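### SAP 7.2 anchors partial adverse-event start dates to the first dose of study drug only, so some UX007 onsets in ex-placebo subjects are dated before UX007

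*SAP*

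**What the plan says.** SAP 7.2 covers both event and medication dates: "The following conventions will be used to impute missing portions of dates for adverse events and concomitant medications". Its start-date limbs, when the year is known, are:

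- Month unknown (b.i): "If the year matches the first dose date year, then impute the month and day of the first dose date". In any other year (b.ii), January is assigned.
- Day unknown (c.i): "If the month and year match the first dose date month and year, then impute the day of the first dose date".
- Day unknown, any other month (c.ii): "Otherwise, assign the first day of the month".

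Section 7.2 does not define the first dose date. SAP 5.4 uses the same term for the start of titration and treatment: "end of period date – first dose date + 1) for the titration and treatment periods". In the placebo group that is a placebo dose.

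SAP 8.7.1 classifies events against two dates. An event is a TEAE "if it occurs or worsens in severity on or after the date of the first dose of study drug". The second class is tied to the first UX007 dose: "An AE will be considered a UX007 emergent adverse event if it occurs or worsens in severity on or after the first date of" that dose. For placebo subjects that date is expected to be "the date of Week 8 visit for the placebo group; however, the date of first UX007 dose actually received will be used".

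SAP 8.1 ends the double-blind period at the Week 8 visit. SAP 8.7.1 reports double-blind TEAEs by treatment group, and SAP 6.5 assigns subjects for that period by the first treatment received.

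**The concern.** The classification uses two dates and the imputation rule knows only one. For a subject who starts on UX007 the two dates coincide, and the rule leans towards calling an event treatment-emergent. For a subject who starts on placebo they are about eight weeks apart. The rule can then place an event that began on UX007 before the first UX007 dose.

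The error runs in one direction. The event leaves the UX007-emergent tables and the numerator of the exposure-adjusted UX007 rates. If the imputed date falls in the double-blind window, the event is also added to the placebo column with which UX007 is compared. Safety through adverse-event rates is a primary objective. At 3:1, about 40/4 = 10 subjects are on placebo, so one subject wrongly added to that column for a given term raises its incidence by about 10 percentage points.

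**Working it through.** The plan states no figure on this point, so there is none to reproduce. The check applies the rule to dates.

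**Inputs.** The limbs are from SAP 7.2. The switch is at day 56 after first dose, with a window of ±3 days (schedule of events). Treatment is followed to day 364 (Week 52). UX007 days in an ex-placebo subject therefore run from day 56 to day 364, which is 309 days. Assumptions: first-dose dates are spread evenly over the calendar, and onsets evenly over UX007 days.

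**Example.** First placebo dose 10 March 2015; first UX007 dose 5 May 2015.

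- Recorded as May 2015: March does not match, so the date becomes 1 May, before UX007.
- Recorded as 2015: the year matches, so the date becomes 10 March, before UX007.

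**Which limbs act.** With a switch at day 53 to 59, the first-dose month and the switch month never coincide. No UX007 day to Week 52 falls under c.i. That limb shows the single anchor; c.ii, b.i and b.ii do the misdating.

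**Day unknown, switch month (c.ii).** If the switch is on day d of a month of length L, that month holds L − d + 1 UX007 days. All are dated to the 1st, before UX007, unless d = 1. Over a 365-day year:

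- UX007 days in switch months: 7×(31×32/2) + 4×(30×31/2) + 28×29/2 = 3472 + 1860 + 406 = 5738, a mean of 5738/365 = 15.7 per subject.
- Days placed correctly (d = 1): 365.
- Share misdated: (5738 − 365)/5738 = 93.6%.
- Share of all UX007 days to Week 52: (5373/365)/309 = 14.72/309 = 4.8%.

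The 1st of the month is at most 30 days before the switch, so it is at least 53 − 30 = 23 days after first placebo dose. Every misdated switch-month event therefore lands in the double-blind window.

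**Month unknown (b.i, b.ii).** Number the start days of a 365-day year x = 0 to 364.

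- x = 0 to 308: the switch is in the first-dose year. The 309 − x UX007 days left in that year are all dated to first placebo dose. Sum: 309×310/2 = 47,895.
- x = 309 to 364: the switch is in the next year. All 309 UX007 days go to 1 January, before UX007, except when the switch is itself on 1 January. Sum: 55×309 = 16,995.
- Share misdated: (47,895 + 16,995)/(365×309) = 64,890/112,785 = 57.5%.

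**Full calendar run.** Every start date over four years, with the switch at day 53, 56 or 59:

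| Switch day | Day unknown, switch month | Day unknown, to Week 52 | Month unknown, to Week 52 |
|---|---|---|---|
| 53 | 93.6% | 4.7% | 57.2% |
| 56 | 93.6% | 4.8% | 57.6% |
| 59 | 93.6% | 4.8% | 58.0% |

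With a second anchor at first UX007 dose, the misdated share of true UX007 onsets falls to 0% in both the switch-month and month-unknown cases.

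**The case against.** The best reply is that partial dates should be few. Events are asked about at every visit, with calls between Extension visits (Protocol 7.5.4.9 and 7.5.4.10). They must be documented promptly (Protocol 8.5.4.1), and incomplete data are queried before lock (SAP 7.1). An event that worsens after the switch still counts as UX007 emergent. Safety is descriptive, with no planned testing (SAP 8.7). All of this stands and limits the size, but 7.2 exists for the dates that remain partial after querying.

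Two textual defences are weaker. SAP 7.1 rules out imputation for open-label analyses, but that sentence closes the rules for seizure outcomes and does not govern event dates. The first dose date is undefined in 7.2, and SAP 5.2 does use a first dose of UX007 within a period. SAP 5.4 nevertheless supports the study-drug reading, and a single anchor at first UX007 dose would instead put some placebo events before study drug.

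Some stronger readings are tempting, and the documents do not support them:

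- A reader might take 44/52 = 85% as the share of year-only events misdated. It is the share of treatment time on UX007. Much of that time can fall in the next calendar year, and the misdated share is 57-58%.
- A reader might say that 10 of 40 subjects are affected. Ten is the number exposed to the rule. Only those with a partial start date in the switch month, or a year-only date, can be affected.
- A reader might say that every misdated event enters the placebo column. That holds for switch-month events. A year-only event under b.i is dated to the first dose itself, and SAP 8.1 starts the double-blind period after the date of the randomization visit. If dosing starts that day, its period is unclear, though it still precedes UX007.

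**Conclusion.** The point holds, within limits. Followed as written, SAP 7.2 dates some true UX007 onsets in ex-placebo subjects before UX007, in the direction that favours UX007. For day-unknown dates the effect is nearly total in the switch month (about 94%) but small over UX007 exposure to Week 52 (about 5%); later months are placed correctly. For month-unknown dates it is about 57-58%.

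The UX007-emergent tables, the exposure-adjusted UX007 rates and the split between double-blind and extension periods are affected. Whole-study TEAE totals are not.

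These shares apply to partial dates only. The documents give no count of them, so the number of events moved cannot be stated and may be small. The shares also assume even spread of start dates and onsets. If onsets cluster soon after the first UX007 dose, the 5% is too low. The conclusion rests on reading the first dose date as first dose of study drug.

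**What to change.** In SAP 7.2, define the first dose date as the date of first dose of study drug. Add one limb for subjects who switch from placebo: impute the date of first UX007 dose if all of the following hold.

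- The known part of the start date is compatible with that date: same month and year when the day is missing, same year when the month is missing.
- The event was not already reported at or before the visit or contact preceding that dose.
- The stop date does not precede that dose.

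The second condition does most of the work. The stop-date check alone is weak, because 7.2 moves partial stop dates to the end of the month or to December. Without the reporting bound, year-only placebo events would be pulled out of the randomised comparison. A true UX007 onset cannot have been reported before the dose, so the bound excludes none of the events that the limb is meant to catch.

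The cost is a few lines in the SAP and the date program, plus the visit or contact of first report for each event with a partial date. The documents do not say whether the adverse-event form holds this; the entry date in the electronic audit trail (Protocol 8.4.1) may serve. The downside is that a few true placebo-period events may be attributed to UX007. That is the conservative direction for its safety tables, and the reporting bound limits it.
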